To compare the overall cost of post-operative rehabilitation of patients involved in traditionally employed regimens versus those using the StepRite device.

Hypothesis and specific aims

The aim of this study is to evaluate whether improved clinical outcomes as well as reduction in cost in provision of care can be better affected through the use of the Steprite device as compared to the use of traditional rehabilitation modalities.

We will seek to reject the null hypotheses that 1) there is no difference between clinical outcomes attained between patients using the Steprite device and those using traditional rehabilitation modalities and that 2) there is no reduction in cost to the medical system when patients use Steprite versus other conventional methods of rehabilitation.

By rejecting the null hypothesis we will accept the alternate hypothesis that, through the use of the Steprite device, not only will patients achieve overall clinical outcomes faster but there will be an associated decrease in cost burden to the medical system and the differences observed will be statistically significant as compared to rehabilitation of patients not using the Steprite device.

Patients who use the device post-surgery will demonstrate superior short-term improvements (i.e. 3 months post-surgery) with respect to self-reported functional outcomes and gait parameters, compared to a control group not using the device. The patients will self-report through the use of validated survey instruments including the KOOS survey (knee injury and osteoarthritis outcome score), LEFS (lower extremity functional scale) and/or KSS (knee society score), the latter of which includes a section for surgeon evaluation of patient functionality post operatively.

Study Design and Methods

This is a point of care clinical trial; a trial that functions to integrate research within a clinical setting that has the ability to readily deliver either modality of the proposal. This type of study design relies on provider referral of patients to be approached for consent, after which randomization to one of two treatment groups is facilitated; a control group of 15 patients participating in conventional rehabilitation regimens and an experimental group of 15 patients who will participate in the same rehabilitation regimen but facilitated

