through the use of Steprite. Importantly, care for patients is delivered as part of current adopted standards utilizing outcome measurements, the use of which and the interpretation of which is already built into care provided by the clinical facility, thereby negating the need to develop additional outcome measures. Recruitment of 30 patients will come from the investigators' normal patient population, among patients who are scheduled for partial or total knee arthroplasty. As there is no change in post op care for these patients from the investigators standard protocols other than monitoring and enforcement of home protocols, the same therapists involved in investigators' normal patient care will be involved with both arms of the study.

For this study, 30 patients represents a sample size deemed acceptable as a starting point. There are no other published studies using Steprite in comparative design trials. Determinations of sample size needed for this study, using 80% power and significance of 0.05, incorporate the use of a time frame in days or weeks for completion of the rehabilitation protocols that would allow for the detection of clinically significant differences between the group using Steprite and those using conventional therapies only. Given that conventional therapies can include skilled nursing, home health and outpatient visits and given that the need for each of these is highly variable dependent on the patient, it is difficult to assign a time value for determinations of sample size.

With that, a sample size of 30 participants divided into two groups represents an initial starting point, with the potential of incremental addition of more patients in order to achieve significance between the two study groups.

Statistical significance will be evaluated utilizing a standard t-test for two group comparison.

In preparation for the study, MedHab Inc. will at their expense train all involved investigators and therapists in the fitting and use of the StepRite device. Medhab will also train a lead therapist designated by the lead investigator to be in charge of overseeing and monitoring, ensuring proper use of the device. There is no cost to the patient, hospital or other funding entity for participation in this study. Medhab LLC will assume all costs associated with the training, application, device and use of the StepRite product for the full course of this study.

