Subjects for this study will be recruited from the patient population seen by the investigators during the normal course of business. There will be no outside recruitment of individuals or advertising as to the presence or use of the monitoring device to entice new patient referral. Prospective candidates will be asked by the lead investigator at the time they are designated surgical candidates. All documentation related to the study will be reviewed with the patient by the lead physician or his designee who is appropriately trained in discussing patient recruitment. Final decision and randomization to control or StepRite use will be done as part of the preoperative checkup just prior to surgery where both operative consent and study consent are discussed and signed.

Randomization:

Once a patient agrees to the study they would be sequentially randomized into whether or not they receive StepRite. The patients will be randomized to every other eligible patient gets the intervention. (ie: 1,3,5,7,9... will get StepRite ; 2,4,6,8 will not get StepRite) 15 Intervention subjects will be recruited and 15 control subjects will be recruited with an extra 5 patients to account for attrition and withdrawals.

Schedule of events

The intervention group will receive the StepRite device with standard conventional care and the control group will receive standard conventional care only. Both groups will receive outpatient, home health, and /or 24 hour physical therapy treatment plans per their surgeon's standard of care. The control group will undergo the conventional outpatient treatment program to 8 weeks as normally prescribed by the lead investigator. This consists of a twice weekly outpatient appointment with a physical therapist and prescribed home exercise program (see attached physical therapy protocol).

The patients randomly selected to wear the StepRite inserts will be fitted and instructed along with the patient's designated care giver in their use including initial pre-op measurements prior to their surgical date so that data collection can begin on the 1st day of rehab after surgery

Those patients not selected to wear step rite will receive instructions preoperatively of their expected therapy regimen and receive their baseline functional evaluation of the knee

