Clinical Trials Coordinator, [name]

[name]

(t)[contact] (f)[contact]

The Research coordinator will fit the patient with the device, pair, and connect the device at time of discharge.

Patient will leave the hospital with the steprite™ device and instructions to charge device overnight for use the next day.

Patient will begin exercise regimen prompted by the StepRite App on the cell phone.

Physical therapy will communicate with the patient per the therapy protocol

Physical therapy is to work with patient per standard of care protocol with the addition of 3 patient outcome surveys, (KOOS, KSS, and the Lower Extremity functional scale) (see attached) at 4, 6, and 8 weeks post op, and the PI will see the patient as standard of care at visits 2, 6, and 12 weeks post-op. The 2 week patient outcome surveys will be completed at the 2 week standard clinic visit with the assistance of the study coordinator. All documents and data collection forms from physical therapy and clinic will be

scanned into the patients chart for review and kept in a locked file cabinet in the research coordinators office 4A144B.

Physical therapy advises the PI and MedHab two weeks prior to close of therapy on close out or extension procedure if needed.

The PI and MedHab extends the therapy or communicates the close out procedure with the patient.

Control Subject flow

The control group will have all Post-op standard of care as the device group without the use of the device.

Device Information

The device to be used in the study is the StepRite, manufactured and supplied by Medhab LLC. The device is considered exempt from IDE regulations, as it is a diagnostic device. It has been approved as a Class I medical device by the FDA.

The StepRite device consists of a thin insole which is placed inside the shoe.

The insole contains pressure sensors which record pressure data when exercises are performed, and contains an accelerometer, which records acceleration of the foot and is used to calculate velocity and activity levels.

A wireless connection between the insole and a cell phone application allows transfer of data.

The cell phone application will be supplied.

The cell phone application displays real-time feedback of pressure distributions to the user, and connects wirelessly to the Medhab servers to upload data onto the secure web interface, for access by the physical therapist or physician.

The device does not impart energy to the user.

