There is a risk of loss of confidentiality, we will have measures in place to help prevent any loss of personal information. During the course of this study there are no new or additional steps required of the subjects from what is considered the standard protocol for the lead investigator. The only alteration may be reduced travel and outpatient visit by the patient if compliance and functional improvement noted by the therapist. StepRite imparts no energy to the patient and poses no hazard to patient well being. Subjects will be free to withdraw from the study at any time and revert to conventional rehabilitation treatment.

Possible benefits to subjects

There is a possibility the device group patient could benefit from the device prompting them to do their own exercises regularly, which could lead to a faster recovery and better physical therapy outcomes. We are hoping the participation in this study may help us learn how we can design rehabilitation programs to be more effective in the future.

Confidentiality measures

StepRite / MedHab will have access to non-PHI patient data collected by the device stored on their HIPPA compliant server and be available only to the lead investigator. All PHI will be kept separate from the study data in a locked filing cabinet or on a password protected computer in the research coordinators office in 4A144B.

Data Collection and Monitoring

Data recorded by the StepRite device will be transmitted wirelessly to the HIPAA secured web interface managed by Medhab. Clinicians will be able to log into the website with a password to review the progress of each patient.

Data recorded by the PI and physical therapist on the functional motion of the knee will be recorded in paper form and kept with the completed KOOS questionnaire and Knee Society Score (KSS) and scanned into the patients HIPPA protected chart.

Upon completion of patient's part in the study MedHab will contact UMC and the Therapy departments to acquire actual costs of these services. This will be done to compare the overall cost of management of the post-operative rehabilitation of a patient in traditional rehabilitative regimen vs. use of StepRite,

Actual Cost information for the patient's full rehabilitation will be requested and collected by the Hospital and released to MedHab at the end of the study and supplied to the lead investigator for analysis.

References

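### The choice of rehabilitation setting has no stated time or criteria, so setting can differ between arms for reasons other than StepRite and blur or bias the cost comparison

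*Combined protocol and SAP*

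**What the plan says.** The second null hypothesis (Hypothesis and specific aims) is that "there is no reduction in cost to the medical system when patients use Steprite versus other conventional methods of rehabilitation". Data Collection and Monitoring defines the measurement: "Actual Cost information for the patient's full rehabilitation will be requested". It names UMC and the therapy departments as the places to be asked. It lists no cost components and no time window.

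For both arms, Schedule of events says "Both groups will receive outpatient, home health, and /or 24 hour physical therapy treatment plans per their surgeon's standard of care". The same section describes the control programme as twice-weekly outpatient appointments to 8 weeks, and later says that subjects are visited by home health therapists. Study Design and Methods lists skilled nursing, home health and outpatient visits as possible parts of conventional care. It declines to derive a sample size, "given that the need for each of these is highly variable dependent on the patient". The only analysis named is a standard two-group t-test.

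Allocation takes place at the pre-operative check-up. Under Randomization, odd-numbered patients get StepRite and even-numbered patients do not. No masking is described.

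The start of device use is given in two ways. Schedule of events has StepRite patients fitted before their surgical date, so that data collection can begin on the first day of rehabilitation. The Device Flow Chart says "The Research coordinator will fit the patient with the device, pair, and connect the device at time of discharge", with therapy starting in the system the day after discharge.

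**The concern.** A stay in a facility may cost several times an outpatient course. In arms of 15, a few such patients can dominate the mean. The plan itself names setting as the large and unpredictable part of rehabilitation. Yet it does not record the intended setting before allocation, balance on it, adjust for it or separate its cost.

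Two problems follow, and they differ in kind. Chance differences in setting between arms widen the error of the cost comparison, so a real saving is likely to be missed. If the arm influences the choice of setting, or if foreseeable alternation influences who is enrolled next, the comparison is biased and a saving could appear without any effect of the device on recovery. Either way, the cost objective may reflect where patients were sent.

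**Working it through.** **The plan's own figure.** The sample size appears beside "using 80% power and significance of 0.05", but no effect size or SD is given; the plan says "it is difficult to assign a time value for determinations of sample size" and that "a sample size of 30 participants divided into two groups represents an initial starting point". The 30 therefore cannot be reproduced. By the normal approximation, 15 per arm has 80% power, two-sided, for a difference of (1.960 + 0.842) × √(2/15) = 1.02 SD (1.06 by the t-test). What inflates the cost SD therefore matters.

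**Assumptions, none from the documents.** Skilled nursing and 24-hour plans are grouped as facility care, although the protocol does not equate them. A facility course costs k = 2 to 10 times a home or outpatient course, which is set to 1. The CV within a setting is 30%. The facility share is varied.

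**Chance imbalance.** Let K of the 30 patients need a facility, with placement unrelated to arm. An even split has probability C(15, K/2)² / C(30, K).
- K = 4: 105² / 27,405 = 0.402, so a gap of 2 or more has probability 0.598.
- K = 6: 455² / 593,775 = 0.349, so 0.651.
- K = 8: 1,365² / 5,852,925 = 0.318, so 0.682.

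These count both directions. For K = 6, about 0.651 / 2 = 33% favour each arm.

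A 4-2 split shifts the difference in mean cost by 2(k − 1)/15. The overall mean at a 20% share is 0.2k + 0.8.

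| k | Shift | Overall mean | Shift as % of mean |
|---|---|---|---|
| 2 | 0.13 | 1.20 | 11% |
| 3 | 0.27 | 1.40 | 19% |
| 5 | 0.53 | 1.80 | 30% |
| 10 | 1.20 | 2.80 | 43% |

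**What this costs in precision (k = 3, 20% share).** Within-setting variance is 0.2 × 0.90² + 0.8 × 0.30² = 0.234. Between-setting variance is 0.2 × 0.8 × 2² = 0.640. The total is 0.874 (SD 0.935), of which 73% comes from setting. A true saving of 20% is 0.28. With 2 × (1.960 + 0.842)² = 15.70:
- Unadjusted: 15.70 × 0.874 / 0.28² = 175 per arm; power at 15 per arm is 13%.
- One setting for everyone: 15.70 × 0.09 / 0.20² = 35.3, so 36 per arm; power at 15 is 45%.
- Adjusted for a recorded plan that predicts setting perfectly (best case): 15.70 × 0.234 / 0.28² = 46.9, so 47 per arm.

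**Arm-dependent choice.** Simulation used 40,000 trials per scenario, 15 per arm, a two-sided t-test at 0.05 and no device effect. The table gives the share of trials with a significant saving for StepRite, across k = 2 to 10 (nominal 2.5%).

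| Facility use, control vs StepRite | Significant saving |
|---|---|
| Equal (20% or 30% in both) | 2.2% to 2.6% |
| 20% vs 10% | 7% to 9% |
| 30% vs 10% | 16% to 25% |
| 30% vs 0% | 35% to 66% |

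The 30% vs 10% case is a gap of 0.20 × 15 = 3 patients. At k = 3 the expected means are 1.6 and 1.2, an apparent saving of 0.4 / 1.6 = 25%. Over k = 2 to 10 it runs from 0.2 / 1.3 = 15% to 1.8 / 3.7 = 49%.

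**The case against.** A reader might infer that setting is always chosen after allocation and before StepRite starts, so that the device cannot have caused any difference in it. The documents do not support this. They do not say when setting is chosen. Controls are told their expected regimen before surgery, so a plan may exist before the arm is assigned. The two accounts of fitting put the start of device use at different points and must be reconciled. Visit numbers and extensions of therapy are decided while the device is in use and may be real effects.

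Some change in setting could also belong to the strategy. Background presents StepRite as part of a treatment model with remote monitoring, and the objective is overall cost. If a surgeon sends a patient home because monitoring is available, that saving is arguably part of what is tested. Against this, Study Design limits the intended difference to monitoring and enforcing home protocols, and Risks mentions only reduced travel and outpatient visits. The protocol leaves the question open.

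The chance calculation does not show bias. With 6 facility patients, the SD of the between-arm count difference is 2 × √(6 × 0.25 × 24/29) = 2.2, so a 4-2 split is ordinary variation that a t-test allows for. This stands: chance imbalance costs precision only. Finally, the documents give no facility share, and entry is limited to ages 45-75 with BMI below 35, so the share could be small.

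**Conclusion.** The point holds as a gap in design and analysis. Setting is discretionary, highly variable by the plan's own account, included in the cost outcome and ignored in the analysis, under foreseeable allocation with no masking described. The loss of precision follows wherever settings are mixed and differ in cost. At k = 3 and a 20% facility share, power for a true 20% saving falls from 45% to 13%. Bias is possible but not shown: it needs setting to depend on arm, or enrolment to depend on the foreseeable next assignment. If it did, a gap of about 3 patients in 15 would raise the rate of false StepRite savings from 2.5% to between 16% and 25%. These sizes rest on the assumed shares, cost ratios and 30% CV. Absence of masking is read from the text's silence and the alternation scheme. This should be corrected, but it does not by itself invalidate the trial.

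**What to change.** 1. Have the surgeon record the planned post-discharge setting when the patient is designated a surgical candidate, before the enrolment number or arm can be known. Collapse it to two levels if needed. By the pre-operative check-up, alternation makes the arm foreseeable, so the record is fully protected only if allocation is concealed.
2. Replace the plain t-test for cost and function with a comparison adjusted for the recorded plan. Do not adjust for actual setting, which may follow allocation. Stratifying on the plan would need a new allocation scheme and is not required here.
3. Keep total rehabilitation cost as the basis for any statement of a saving. Home health plus outpatient cost cannot decide it, because that sum also depends on actual setting: an arm with more facility patients could look cheaper on it.
4. Request costs by component. Confirm whether skilled nursing and home health costs from outside UMC and the therapy departments are captured. Report components and actual setting by arm, beside planned setting, as description only. Adjustment cannot remove departures from the plan that depend on arm, but this table would show them.
5. State when and by what criteria setting is chosen. Reconcile the two descriptions of device fitting, and the outpatient control programme with the open choice of setting.

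The cost is one extra form line, a more detailed cost request, revised analysis wording and one covariate in a 30-patient trial. Concealed allocation would be a separate change.

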Both groups will be given log sheets to record their activity at home and when seen by the physical therapist. These will be returned and collected by the therapist weekly and scanned into/ kept in the patient's medical record file. A paper copy will be kept in the coordinator's office, 4A144B with the consent forms and any other study documents.

Both groups will also have routine self-assessment questionnaires (appendices 3, 4 KOOS and KSS) and functional testing performed by the PI and PT during the patient's regular clinic visit as standard of care.

Outcome measurements performed just after surgery and at time of discharge from hospital and standard of care post-surgical clinic visits to 8 weeks will indicate if any patients are experiencing unexpected delays in progress. Subjects will be visited at home by the Home Health therapists, and will visit and receive telephone consultations with the outpatient therapists, who will be able to monitor the patients' conditions and intervene if there are any problems related to the use of the device. The StepRite device will provide the therapist with more information about the patients' activity levels and progress than would usually be available to them and so is not expected to have any safety implications. The device and App. will prompt the patient with voice and text to complete their exercises as they are needed, while collecting data.

Device Flow Chart: standard of care post-op

The research coordinator will consent the patient prior to the surgery

The research coordinator will document the following information for the device on the device data collection form. (See attached)

- a. Name of patient
- b. Email of patient
- c. Phone number of patient
- d. Surgery date
- e. Expected date of discharge

The patient's information will then be entered into the steprite™ system and a patient account will be created by the Research Coordinator

Physical therapy will schedule the study protocol via the steprite™ system and enter the physical therapy start date as day after discharge.

MedHab™ sponsor ([name]) will contact the patient for the patient account set up and to obtain the following signatures required by MedHab (see attached)

- a. HIPAA
- b. Assignment of Benefits

MedHab™ will help the patient load the app, provide an overview of the app, and forward a tutorial video
MedHab™ will send the steprite™ device to the study Research Coordinator at TTUHSC

TTUHSC Orthopaedic Surgery

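### No common baseline before allocation is defined and no pre-operative KOOS, LEFS or KSS is explicitly scheduled, so change from before surgery and baseline adjustment are not assured

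*Combined protocol and SAP*

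**What the plan says.** Hypothesis and specific aims: patients using the device "will demonstrate superior short-term improvements (i.e. 3 months post-surgery) with respect to self-reported functional outcomes and gait parameters" compared with controls. The instruments named are KOOS, LEFS and/or KSS.

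Study Design and Methods: allocation takes place at the preoperative checkup. The only analysis named is a two-group t-test, with no change score and no covariate. The Randomization section sets strict alternation, with odd-numbered patients receiving the device.

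Schedule of events: pre-operative assessment is described for patients whose arm is already settled.

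- Device patients are fitted and instructed, "including initial pre-op measurements prior to their surgical date so that data collection can begin on the 1st day of rehab after surgery".
- Patients not selected for the device are told what therapy to expect and "receive their baseline functional evaluation of the knee".
- Later in the section, both groups have KOOS, KSS and functional testing at regular clinic visits. No time point is given and LEFS is not listed.
- The section also refers to "Outcome measurements performed just after surgery and at time of discharge from hospital and standard of care post-surgical clinic visits to 8 weeks", without naming instruments.

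Device Flow Chart: KOOS, KSS and LEFS are dated at 4, 6 and 8 weeks, with a 2-week set completed in clinic. It also states: "The Research coordinator will fit the patient with the device, pair, and connect the device at time of discharge".

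**The concern.** Improvement needs a starting value. For the self-reported scores, the plan gives no dated measurement before surgery. The earliest dated survey, at 2 weeks, is a poor substitute: the flow chart starts therapy the day after discharge, so a 2-week score may already reflect the intervention, and adjusting for it could remove part of the effect under test.

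The pre-operative text does not fill the gap. It is written separately for each arm, defines neither assessment, and places both after the arm is known. The device arm's measurement is itself uncertain, because one section has the inserts fitted before the surgical date and another at discharge.

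Three things are at stake:

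- the hypothesised change in self-reported function may have no common starting point;
- the precision that a baseline covariate would bring is lost in a trial of 15 per arm;
- there is no assured way to check that the arms started alike, and this matters more than usual because alternation lets staff foresee the next assignment.

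A pre-operative score cannot be recovered after surgery.

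**Working it through.** **The plan's own figure.** The protocol mentions "Determinations of sample size needed for this study, using 80% power and significance of 0.05" but gives no effect size or SD; it says "it is difficult to assign a time value for determinations of sample size" and that "30 patients represents a sample size deemed acceptable as a starting point". The total of 30 therefore cannot be reproduced. The attrition allowance is consistent: 5/35 = 14.3%, and 30/(1 − 5/35) = 35.

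**Is a pre-operative survey scheduled?**

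| Assessment | Section | Timing | Same in both arms? |
|---|---|---|---|
| KOOS, KSS, LEFS | Device Flow Chart | 2, 4, 6, 8 weeks post-op | Yes, if the control flow is read as matching |
| KOOS, KSS, functional testing | Schedule of events | Undated | Yes; LEFS not listed |
| Outcome measurements, instruments not named | Schedule of events | From just after surgery to 8 weeks | Not stated |
| Initial measurements (device arm) | Schedule of events | Pre-op, after allocation | Not stated |
| Functional evaluation of the knee (control arm) | Schedule of events | Pre-op, after allocation | Not stated |

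No row is a dated pre-operative KOOS, LEFS or KSS.

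**Detectable difference without a baseline.** Inputs from the protocol: 15 per arm, 80% power, significance 0.05. Two-sided testing is an assumption, as sidedness is not stated.

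- Normal approximation: (1.960 + 0.842) × √(2/15) = 2.802 × 0.365 = 1.02 SD.
- Noncentral t: 1.06 SD (0.93 SD if one-sided).

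**Detectable difference with a common pre-operative score.** The correlation r between pre-operative and follow-up scores is not in the documents; 0.3 to 0.7 is assumed. Analysis of covariance multiplies the SD by √(1 − r²), and a change score by √(2(1 − r)). Estimating the covariate slope with 30 patients inflates the variance by about 1 + 1/26 on average, which multiplies the detectable difference by √(27/26) = 1.019.

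| r | 1 − r² | ANCOVA: 1.06 × √(1 − r²) | After slope cost (× 1.019) | Change score: 1.06 × √(2(1 − r)) |
|---|---|---|---|---|
| 0.3 | 0.91 | 1.01 SD | 1.03 SD | 1.25 SD |
| 0.5 | 0.75 | 0.92 SD | 0.94 SD | 1.06 SD |
| 0.7 | 0.51 | 0.76 SD | 0.77 SD | 0.82 SD |

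In patient numbers, 30/(1 − r²) is 33, 40 and 59. Dividing by 27/26 gives about 32, 39 and 57.

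For an assumed true difference of 0.8 SD, power is 56% on follow-up scores alone and 60%, 69% and 84% with ANCOVA (before the slope cost). A change score helps only when r exceeds 0.5, so ANCOVA is the better use of the baseline.

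**Chance imbalance.** Even under sound randomisation, the difference in mean baseline has standard error √(2/15) = 0.37 SD. The probability that it exceeds 0.5 SD in either direction is 2 × (1 − Φ(0.5/0.365)) = 2 × (1 − Φ(1.37)) ≈ 17%.

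**The case against.** The strongest reply is that the protocol may intend a baseline without dating it. The routine KOOS and KSS at regular clinic visits could include a pre-operative visit. The 2-to-8-week list sits under a heading about post-operative care, so its silence about the period before surgery is weak evidence. The appended forms might also settle the matter. This stands in part: it rules out saying that no baseline will be collected. It does not make one planned, and it leaves LEFS uncovered.

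A reader might infer that the arms receive different baseline measurements. The documents do not show that. Neither assessment is defined, and both groups have functional testing as routine care. What is shown is that the assessments are not stated to be the same.

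A reader might also infer that improvement cannot be computed, or that the main comparison fails. That goes too far. The formal null concerns clinical outcomes attained, and a comparison of post-operative scores needs no baseline. Nor does cost, or the time to complete rehabilitation that the sample size text discusses. Measuring after allocation but before surgery mainly risks unblinded assessment; it does not prevent a change score.

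Finally, a t-test is not an error. Under valid randomisation its standard error already covers chance imbalance, so the loss is precision rather than bias. This stands. Bias could arise from the predictable alternation, which is a separate defect; the link here is that common baseline scores are what would allow its effect to be examined.

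**Conclusion.** The point holds as a gap in the plan, not as proof that the trial cannot answer its question. No common baseline before allocation is defined, no pre-operative KOOS, LEFS or KSS is explicitly scheduled, and no adjusted analysis is named. Change from before surgery in self-reported function is therefore not assured, and neither are baseline adjustment and a check of comparability under alternating allocation.

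The size of the precision loss depends entirely on the assumed correlation. At r = 0.3 the gain forgone is small (1.06 to 1.03 SD after the slope cost). At r = 0.7 it is substantial (1.06 to 0.77 SD, roughly the information from 57 patients instead of 30). These figures assume two-sided testing and 15 analysed per arm, and they measure lost precision only; they do not quantify unblinded assessment or selection through alternation.

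The plan should be changed before enrolment, because the missing score cannot be obtained later. A related gap bears on the same hypothesis: it is set at 3 months, while the dated surveys stop at 8 weeks although a 12-week clinic visit is planned.

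**What to change.** 1. At the existing preoperative checkup, after consent and before the arm is assigned or revealed, have every patient complete KOOS, LEFS and the patient part of the KSS and receive the same defined functional evaluation of the knee. State this once, for both arms. While allocation alternates, staff can still foresee the arm, so the order of events protects the assessment only in part.
2. Replace the t-test for these scores with analysis of covariance: follow-up score on arm and the pre-operative value of the same score. Report the pre-operative scores by arm.
3. Reconcile Schedule of events with the Device Flow Chart on when the device is fitted, so that any device-based baseline has one stated time.

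The cost is one extra questionnaire set per patient, a knee evaluation common to both arms at a visit that already takes place, and one covariate (one degree of freedom) in the analysis.
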